3.6.3 Data handling

The procedures will be conducted in compliance with our standards for AF ablations and as specified in appendices A and B. All data to be analyzed in this study will be generated within the framework of this study protocol. There will be no transfer of data from the patient's hospital files to the study other than data generated as part of this study

PeAF box feasibility ver 2.3Descriptive data:

Feasibility: Time consumption (min.), use of X-ray (mGy), ablation time (min.) and energy delivery (watt x sec.) are registered when WACA-PVI is completed and compared to the same values at the end of the procedure. An estimate of the percentage increase of the procedure parameters due to the added LAPWI will be calculated. In the event that LAPWI cannot be achieved within *20 min additional ablation time* after WACA-PVI then LAPWI will be considered *not achievable*.

Safety: The unlikely occurrence of pericardial effusion will be estimated and measured by TTE from subxiphoid and parasternal windows immediately after the procedure and compared to preprocedure echo measurements.

Durability: At the follow-up procedure after 3 months a single transseptal puncture will be done and the durability of bidirectional block of the PV's and the LAPW will be checked with a soft 20 polar catheter (Pentarray®). If electrical conduction gaps in the ablation lines are detected a second TS puncture will be performed and an ablation catheter inserted into the LA. Then the precise localization of gaps will be noted and related to the data from the index procedure (force-time integral, ablation index, esophagus temperature) for each point before gap closure with RFA. **Secondary aims (paragraph 3.3):** The patients will be asked to answer the AFEQT 20 item validated questionnaire³⁴ (see ref.; full questionnaire not append in protocol) on quality of life in patients with atrial fibrillation prior to the ablation and at 3, 6 and 12 months post ablation. The implanted ILR will be programmed to diagnose AF and AF related arrhythmias with the best achievable sensitivity and specificity. There will be a routine reading and clearing of device at 1, 3, 6, 9 and 12 months after the index procedure. Further the patients will be instructed to have the device read if they experience palpitations or other AF related symptoms.

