3.8 Risks, inconvenience and patient exposure to adverse events

A) Since participating patients are all scheduled for PVI the added risk relate to the elements added by the study protocol. Directly related to the procedure are: 1) Added ablation (LAPW) compared to PVI alone. This increases the amount of ablation with estimated 30%, increases the total procedure time with an estimated 10% and increases the total fluoroscopy dose area product (DAP) with an estimated 5-10%. 2) A mandatory second procedure after 3 months. This procedure will be minor in most patients.

B) Risk to the oesophagus. Although inflammatory reactions and even devastating fistulae after ablation at or near LAPW are mentioned in the literature (including recently). We have never in our setting (15 years) experienced any clinical manifestations of damage to the oesophagus when performing ablation procedures - including PVI + BOX lesion sets. On the other hand this has not been studied systematically with oesophagoscopy. Thus the detection of subclinical superficial in-

PeAF box feasibility ver 2.3

flammation of the oesophageal wall in this study is a possibility and is in fact *the pivotal safety parameter under study*. The oesophagus temperature is monitored closely with a temperature probe during the procedures and the ablation process is tailored to avoid damage.

C) X-ray exposure. It is estimated that adding BOX to PVI in the first procedure will add extra 0,5 mSv. and the obligatory follow up procedure after 3 months an extra 3-4 mSv. This might increase the lifetime risk of developing mortal cancer from around 45% to 45,01 % (one in 10000 pts.).

D) Implantation of loop recorder (ILR). Is a minor surgical maneuver with subcutaneous insertion of a chip measuring 2 mm * 3 mm * 40 mm performed while the patient is still under full anesthesia at the end of the ablation procedure. The overall rate of adverse events related to that device is an estimated 1% - 2% including pain and local infection.

E) Oesophagoscopy the day after the procedure. This is a common invasive routine procedure performed by a highly skilled gastroenterologist. International literature estimates the overall complication rate to around 0,1%. However up to 2 % of patients may experience soreness of throat or annoying belching post procedure. The procedure is done under light sedation and overall this added oesophagoscopy is estimated to delay discharge for two hours.

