Appendix A. PeAF-BOX - feasibility. Flow-sheet

PeAF screening

Eligible + informed consent

Amiodarone: Continue or start for a run -in period of 3 weeks prior to procedure. No other class 3 or class 1 AAD allowed

Day 0 WACA-PVI + LAPWI procedure incl. cardioversion if necessary

Prove bidirectional PVI and LAPWI incl. adenosine test for dormant conduction

Wait 30 minutes and test bidirectional PVI and LAPWI again

Close gaps and prove bidirectional PVI and LAPWI

Implant ILR

TTE immediately post procedure

[figure not shown]
Day 1 Oesophagoscopy

Day 28 Stop amiodarone

Day 90 Mandatory re-procedure
 - Test PVI + LAPWI , identify, characterize, close gaps
 - if symptomatic arrhythmias after day 60 diagnose and ablate

Day 180 Symptom score

Day 360 Symptom score

[figure not shown]

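### The procedure-time increase attributed to LAPWI also counts shared testing, a fixed 30-minute wait and pulmonary vein gap closure, so it does not isolate LAPWI work

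*Combined protocol and SAP*

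**What the plan says.** Section 3.2 makes feasibility a primary aim, stated descriptively: isolation of the posterior wall should be possible with a reasonable increase in procedure, ablation and fluoroscopy time. Section 3.6.3 gives the measure. Four parameters (time, X-ray use, ablation time and energy) "are registered when WACA-PVI is completed and compared to the same values at the end of the procedure". It continues: "An estimate of the percentage increase of the procedure parameters due to the added LAPWI will be calculated". The only numerical feasibility limit is "20 min additional ablation time", after which LAPWI counts as not achievable.

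Appendix A sets out Day 0. After the combined ablation step come, in order:

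- a demonstration of block for both lesion sets, with adenosine to unmask dormant conduction
- the pause and second check, given as "Wait 30 minutes and test bidirectional PVI and LAPWI again"
- closure of any gaps found, in either lesion set, and a further demonstration of block for both
- ILR implantation
- TTE, described as immediately after the procedure.

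Section 3.8, item A, estimates that the added LAPW ablation, compared with PVI alone, raises total procedure time by 10%. Item D places ILR implantation as "performed while the patient is still under full anesthesia at the end of the ablation procedure".

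**The concern.** The measure is a before-and-after difference within each patient, and the whole difference is given to LAPWI. That is sound only if everything between the two readings is LAPWI work. On the flow sheet it is not: the adenosine test, the wait, the re-test and the gap closure serve both lesion sets. No section subtracts them, and no reading is taken when LAPWI is complete.

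This matters because no threshold is set for procedure time, so readers will judge from the reported percentage whether the prolongation is reasonable. The aims at the end of section 2.3 also say that the data will help to design a randomized comparison of PVI with PVI plus LAPWI. The time difference between those arms depends on how much of the window is LAPWI and how much both arms would share.

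**Working it through.** **1. What lies in the window.** Section 3.6.3 and Appendix A, read together, give the following.

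| Step after WACA-PVI | Serves | Duration in the documents |
|---|---|---|
| Roof and inferior lines | LAPWI | Not given (limit of 20 min ablation time) |
| Adenosine test and proof of block | PVI and LAPWI | Not given |
| Wait | PVI and LAPWI | 30 min |
| Re-test | PVI and LAPWI | Not given |
| Gap closure and renewed proof | PVI and LAPWI | Not given |
| ILR implantation | Neither | Not given; may fall inside or outside |

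Both section 3.6.3 and Appendix A put the TTE immediately after the procedure, and Appendix A lists it last. On that order the procedure ends after the wait and the gap closure.

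**2. Which parameters are affected.** The wait adds elapsed time. Ablation time and energy are affected only when vein gaps are closed, and X-ray use only when fluoroscopy is used in a shared step.

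**3. The protocol's own figure.** The 10% estimate cannot be reproduced, because the documents give neither a PVI duration nor a LAPWI duration. It can be checked for consistency with the planned measure. Let P be the elapsed minutes at the WACA-PVI reading and L the minutes of LAPWI work. Counting only LAPWI and the wait, the reported increase is

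(L + 30) / P.

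For this to be no more than 0.10, L must be no more than 0.10P − 30. Since L cannot be negative, P must be at least 30 / 0.10 = 300 min. With an illustrative L of 20 min, P must be at least 50 / 0.10 = 500 min. So for any PVI phase shorter than 300 min the planned measure exceeds 10%, even if LAPWI takes no time. This step needs no assumed PVI duration.

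**4. Size if a PVI-only procedure would include the same wait.** The consistent comparison then removes the wait from the increment and adds it to the PVI-alone time: L / (P + 30). P and L below are assumptions, not figures from the documents.

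| P (min) | L (min) | Reported (L+30)/P | Consistent L/(P+30) | Difference (points) |
|---|---|---|---|---|
| 300 | 30 (10% of P) | 20.0% | 9.1% | 10.9 |
| 180 | 18 (10% of P) | 26.7% | 8.6% | 18.1 |
| 90 | 9 (10% of P) | 43.3% | 7.5% | 35.8 |
| 300 | 20 | 16.7% | 6.1% | 10.6 |
| 180 | 20 | 27.8% | 9.5% | 18.3 |
| 90 | 20 | 55.6% | 16.7% | 38.9 |

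Joint testing, vein gap closure and any ILR time inside the window come on top; no durations are given for them.

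**5. Size if a PVI-only procedure would have no wait.** The wait is then a real cost of the combined procedure and contributes no overstatement. Vein testing, vein gap closure and any ILR time in the window are still labelled as LAPWI.

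**The case against.** The strongest objection is that the bias from the wait depends on a fact that the documents do not give. No section says whether PVI alone at this center includes a 30-minute wait. Section 3.8 says "Since participating patients are all scheduled for PVI the added risk relate to the elements added by the study protocol" and does not list the wait, but that list is about risk and inconvenience. It also leaves out the adenosine test and the TTE, so the omission is weak evidence. Section 2.3 lists waiting time with adenosine testing among general procedural improvements, which suggests that it is not specific to LAPWI but does not settle the PVI-only workflow. This objection stands: the wait's contribution is anywhere from 0 to 30 minutes.

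A second objection is that the 10% estimate may show that the authors never meant the wait to count, so the fault is only in undefined time points. That is possible. The start is largely implied, since section 3.2 speaks of established WACA-PVI, but the end is not defined. Reading the end as completion of LAPWI is strained, given where the TTE falls. If that is nevertheless the intention, it has to be written down.

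Third, the figure is descriptive and partly recoverable. A reader can subtract a fixed 30 minutes, and the point-by-point registration in Appendix B allows vein touch-up ablation time and energy to be separated. This also stands in part. The elapsed time of joint testing and vein gap closure cannot be recovered from what is planned.

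A reader might go further and infer that LAPWI time will be overstated by 30 minutes, or by at most 30 minutes. Neither follows: the wait's share may be zero, and 30 minutes bounds the wait alone, not the testing and gap closure. Nor should the wait be measured against the 20-minute limit, because one is clock time and the other is ablation time.

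**Conclusion.** The point holds in a limited form. Followed as written, the plan charges joint testing and vein gap closure to LAPWI, and also the 30-minute wait to the extent that PVI alone would include it. If the wait is in the window, the planned measure and the 10% estimate in section 3.8 cannot agree for any PVI phase under 300 minutes.

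The firm results are the content of the window, the 0 to 30 minute range for the wait and the 300-minute threshold. The percentage-point differences (about 11 to 39 in the cases shown) rest on an assumed PVI phase of 90 to 300 minutes, assumed LAPWI times, and the condition that PVI alone includes the full wait. They illustrate scale and are not estimates for this center.

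The consequence is mainly for one descriptive procedure-time figure under a primary aim. It would be tempting to conclude that the feasibility classification or the safety test is compromised. The documents do not support that: the 20-minute limit counts ablation time, and the esophageal hypothesis and the sample size of 23 do not use procedure time.

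**What to change.** In section 3.6.3:

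- Define when WACA-PVI counts as completed, and define the end of the procedure as the final proof of block, before ILR implantation.
- Add one reading of the four parameters at first LAPWI block, or when the existing 20-minute limit is reached. Take it before the joint adenosine test and the wait; a reading after the joint test would still contain shared work.
- Report the LAPWI increment as that reading minus the WACA-PVI reading, plus any later roof or inferior-line ablation identified from the Appendix B point annotation.
- Report the wait, the shared testing and the vein gap closure separately, beside the total increase.
- State the denominator of the percentage. If a PVI-only procedure would include the shared steps, add them to the PVI-alone time; if not, say so.

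The cost is one extra reading per procedure in 23 patients, a note of the clock time spent on the shared steps, and a changed formula. There is no additional procedure and no change to treatment.

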3.7 Statistical Considerations

There will be no randomization or direct between-groups comparisons. Although this study is primarily exploratory and descriptive in nature we will formally test the hypothesis given in paragraph 3.4. Thus the sample size calculation of this study hinges on the need to demonstrate - with a reasonable power - that putative esophageal reactions to the WACA-PVI + LAPWI procedure do not exceed earlier findings after PVI alone.

PeAF box feasibility ver 2.3Calculation of sample size and power:

a) The outcome of esophagoscopy on day 1 after ablation in the LA is considered to be either positive (inflammation or other esophageal reaction is noted) or negative (no reaction). Therefore the probability distribution of outcomes of esophagoscopy will behave binomially.

b) Recent data indicate that esophageal reactions can be observed in the range of 10 % (proportion = 0.1) up to 30 % (proportion = 0.3) with the second generation ablation technology. We would be interested in showing that the proportion of esophageal reactions to WACA-PVI + LAPWI does not exceed proportions reported earlier (i.e. render probable that the proportion of any visible esophageal reaction to ablation is less than 0.3)

c) Setting as comparator that the underlying proportion (P) of patients subjected to this treatment that experience esophageal reactions is 0.3 or more AND assuming that the "true" proportion in our study is 0.1 then when:

- P =	0.3
- One-tailed α =	0.05
- "true" proportion =	0.1

- recruiting 23 patients will yield 80 % power to reject the (H_0) hypothesis that the proportion experiencing esophageal reactions is equal to or higher than the 0.3.

Based on these calculations we aim to recruit 23 patients for the study.

The above computations were aided by the software program (IBM/ SPSS - Sample power ® ver. 3.0.1)

Post - hoc analyses: Statistical analysis of input - and output data will be performed using IBM/SPSS ® ver. 22 using appropriate statistical methods.

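### With 23 patients the oesophageal safety test cannot have both a one-tailed alpha of 0.05 and 80% power: the exact test has 59% power, and the cut-off that reaches 80% has an alpha of 0.054

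*Combined protocol and SAP*

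**What the plan says.** Section 3.7 (Statistical Considerations) treats each day-1 oesophagoscopy as positive or negative and concludes: "Therefore the probability distribution of outcomes of esophagoscopy will behave binomially". The null hypothesis is that "the proportion experiencing esophageal reactions is equal to or higher than the 0.3". The planning assumption is that the true "proportion in our study is 0.1 then when" the error rate is set at "One-tailed α = 0.05". From these inputs the section states that "recruiting 23 patients will yield 80 % power to reject the (H_0) hypothesis" and closes: "Based on these calculations we aim to recruit 23 patients for the study".

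Sections 3.4 and 3.7 name no test statistic and give no number of positive endoscopies at which H0 would be rejected. The only sentence about analysis methods, under the post-hoc heading of 3.7, promises an analysis "using appropriate statistical methods". Section 3.8, item B, calls oesophageal inflammation "the pivotal safety parameter under study".

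**The concern.** The number of positive endoscopies out of 23 is a whole number, so only a few pairs of alpha and power are available. The stated pair of 0.05 and 80% looked like the output of a continuous approximation rather than something 23 binomial outcomes can deliver.

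This is the study's only formal hypothesis test and the sole basis for its sample size. If the test is exact, the chance of missing a true rate of 0.1 is about twice the stated 20%. If the cut-off is loosened to recover the power, the type I error exceeds the stated limit. With no test or cut-off fixed in advance, the choice between the two could be made after the count is known.

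**Working it through.** **Inputs, all from section 3.7:** n = 23, null proportion p0 = 0.3, assumed true proportion p1 = 0.1, one-tailed alpha 0.05, stated power 80%.

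**1. Reproducing the stated 80%.** The arcsine approximation gives power = Φ(h√n − 1.645), where h = 2·arcsin√p0 − 2·arcsin√p1.

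- h = 1.1593 − 0.6435 = 0.5158
- h√23 = 2.474
- power = Φ(2.474 − 1.645) = Φ(0.829) = 79.6%

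The sample size this formula needs for 80% power is 23.2, so it accounts for the plan's figures. Other one-sided approximations at n = 23 differ: 75.3% for the normal (score) formula using the null and alternative variances, and 63.2% with a continuity correction.

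**2. Exact operating characteristics.** Let X be the number of positive endoscopies, binomial with n = 23. For the rule that rejects H0 when X ≤ c, the actual alpha is P(X ≤ c | 0.3) and the power is P(X ≤ c | 0.1).

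| Reject H0 if X is at most | Actual alpha (p = 0.3) | Power (p = 0.1) |
|---|---|---|
| 1 | 0.0030 | 31.5% |
| 2 | 0.0157 | 59.2% |
| 3 | 0.0538 | 80.7% |
| 4 | 0.1356 | 92.7% |

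The step from 2 to 3 adds P(X = 3 | 0.3) = 0.0382 to alpha and P(X = 3 | 0.1) = 0.2153 to power. No row has alpha of at most 0.05 together with power of at least 80%. Any non-randomised test that rejects for low counts corresponds to one such cut-off, so choosing another test only selects a different row.

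**3. The result at the boundary, 3 of 23 (0.1304).** The null standard error is √(0.3 × 0.7 / 23) = 0.0956.

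| Test | Calculation | One-sided p | Rejects at 0.05? |
|---|---|---|---|
| Exact binomial | P(X ≤ 3 given 0.3) | 0.054 | No |
| z with continuity correction | (0.1304 + 1/46 − 0.3) / 0.0956 = −1.55 | 0.061 | No |
| Score z | (0.1304 − 0.3) / 0.0956 = −1.77 | 0.038 | Yes |
| Wald z | (0.1304 − 0.3) / √(0.1304 × 0.8696 / 23) = −2.41 | 0.008 | Yes |

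The exact one-sided 95% upper limit at 3 of 23 is 0.304. A score test could therefore declare the rate below 0.3 while the exact limit still included 0.3.

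**The case against.** The strongest reply is that 80% is not a slip. It follows from a standard approximation, and section 3.7 says the figures came from sample-size software. Saying that outcomes are binomial describes the data and does not commit the plan to an exact test. The uncorrected score, Wald, mid-p and arcsine tests would all reject at 3 of 23. With any of them the power is 80.7% and alpha exceeds 0.05 by only 0.0038. Section 3.7 also calls the study mainly exploratory and descriptive, and the choice of test decides the verdict at only one count.

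Much of this is fair. The figure is an approximation used where it is too coarse, and an openly declared cut-off of 3 would be defensible in a study of this kind. The sentence on appropriate methods sits under the post-hoc heading, so it is weak evidence of how the formal test would be run. The missing test and cut-off are the stronger evidence.

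The reply does not rescue the stated pair. An approximation cannot change what 23 binomial outcomes deliver, and even on the favourable reading the stated alpha is not met. The single ambiguous count is also not rare: its probability is 21.5% under the plan's own assumption. It is also true that a larger sample would meet both targets. The smallest is 28, rejecting at 4 or fewer, with alpha 0.0474 and power 85.8%. That is a different design, and it is not needed to make the present one accurate.

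**Conclusion.** The concern holds. With 23 patients the plan cannot have both error rates that it states. Under an exact test at the 0.05 level, the type II error is 41% rather than 20%, so power is overstated by about 21 percentage points (80 − 59.2 = 20.8). Under a cut-off of 3, power is as stated but the one-sided alpha is 0.054. Because neither test nor cut-off is named, the conclusion at 3 of 23 is open to a choice made after the result is seen.

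The calculation takes the plan's null rate and assumed true rate as given, and assumes 23 independent, evaluable endoscopies. Section 3.4 defines the hypothesis for patients after a successful procedure, and no allowance for fewer evaluable patients is stated. With 22 evaluable, the cut-off of 3 would have an alpha of 0.068.

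**What to change.** In section 3.7, name the one-sided exact binomial test and state its rejection rule as a count. Choose one of two options before any endoscopy results are seen:

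- **Keep alpha at or below 0.05:** reject H0 if 2 or fewer of 23 are positive. State the actual alpha as 0.016 and the power at a true rate of 0.1 as 59%.
- **Keep about 80% power:** reject H0 if 3 or fewer of 23 are positive. State the actual one-sided alpha as 0.054 and the power as 81%.

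Under either option, report the observed proportion with its exact confidence interval. The cost is protocol wording, together with a less favourable stated power or alpha. No extra patients are needed.

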3.8 Risks, inconvenience and patient exposure to adverse events

A) Since participating patients are all scheduled for PVI the added risk relate to the elements added by the study protocol. Directly related to the procedure are: 1) Added ablation (LAPW) compared to PVI alone. This increases the amount of ablation with estimated 30%, increases the total procedure time with an estimated 10% and increases the total fluoroscopy dose area product (DAP) with an estimated 5-10%. 2) A mandatory second procedure after 3 months. This procedure will be minor in most patients.

B) Risk to the oesophagus. Although inflammatory reactions and even devastating fistulae after ablation at or near LAPW are mentioned in the literature (including recently). We have never in our setting (15 years) experienced any clinical manifestations of damage to the oesophagus when performing ablation procedures - including PVI + BOX lesion sets. On the other hand this has not been studied systematically with oesophagoscopy. Thus the detection of subclinical superficial in-

PeAF box feasibility ver 2.3

flammation of the oesophageal wall in this study is a possibility and is in fact *the pivotal safety parameter under study*. The oesophagus temperature is monitored closely with a temperature probe during the procedures and the ablation process is tailored to avoid damage.

C) X-ray exposure. It is estimated that adding BOX to PVI in the first procedure will add extra 0,5 mSv. and the obligatory follow up procedure after 3 months an extra 3-4 mSv. This might increase the lifetime risk of developing mortal cancer from around 45% to 45,01 % (one in 10000 pts.).

D) Implantation of loop recorder (ILR). Is a minor surgical maneuver with subcutaneous insertion of a chip measuring 2 mm * 3 mm * 40 mm performed while the patient is still under full anesthesia at the end of the ablation procedure. The overall rate of adverse events related to that device is an estimated 1% - 2% including pain and local infection.

E) Oesophagoscopy the day after the procedure. This is a common invasive routine procedure performed by a highly skilled gastroenterologist. International literature estimates the overall complication rate to around 0,1%. However up to 2 % of patients may experience soreness of throat or annoying belching post procedure. The procedure is done under light sedation and overall this added oesophagoscopy is estimated to delay discharge for two hours.

F) Adverse effects from amiodarone treatment. Amiodarone is a highly effective and much used antiarrhythmic drug with many potential adverse effects. Most important are effects on the thyroid hormone synthesis due to the many iodine residues in the molecule. Patients with former adverse reactions/ experiences with the drug will be excluded from participation and patient who do not tolerate the drug in the 3 week run-in period pre procedure will also be excluded and treated by other means. The remaining patients who do not experience adverse effects during run-in will continue the drug for 3 weeks post procedure to stabilize sinus rhythm for one to two months.

3.9 Research ethical considerations.

This study is a part of the continuing effort to increase accessibility, efficiency and safety of catheter ablation in persistent atrial fibrillation (PeAF) which is notoriously difficult to treat both pharmacologically and invasively. Patients more often than not need more than one procedure to get rid of the disease. This study aims to establish the feasibility and safety of adding a second ablation element to the primary procedure in order to avoid the need for secondary procedures. Further we will evaluate by long term follow-up the efficacy. Patients scheduled for ablation of PeAF will be asked to give informed consent and participate. Participating patients will be exposed to several inconveniences and adverse effects (given in **paragraph 3.8**).

On the other hand participants will be followed very closely for symptoms or signs of recurrent arrhythmia and gain access to immediate qualified treatment. Further there is a possibility that the participating patients (PVI + BOX) will fare better and need fewer secondary procedures compared to non-participants (PVI only). Atrial fibrillation is a large and increasing disease entity worldwide. Therefore every well conducted collection of data on new methods/ approaches may importantly impact the treatment of these patients worldwide

PeAF box feasibility ver 2.3

It is the perception among the participating scientists that we, by conducting this study, can safely and in a routined manner obtain important data and still maintain *both* a favorable benefit/risk ratio for the participants *and* a favorable benefit/cost ratio to the surrounding society.

